6.1 SCREENED POPULATION

The Screened Population will consist of all patients who underwent a Screening Visit and received a screening number, and for whom informed consent was obtained.

6.2 RANDOMIZED POPULATION

The Randomized Population will consist of all patients in the Screened Population who were randomized to a treatment group in the study.

6.3 SAFETY POPULATION

The Safety Population will consist of all patients in the Randomized Population who received at least 1 dose of double-blind investigational product.

6.4 INTENT-TO-TREAT POPULATION

The Intent-to-Treat (ITT) Population will consist of all patients in the Safety Population who had the baseline and at least 1 postbaseline assessment of the CDRS-R total score.

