9.2 MEASUREMENT OF TREATMENT COMPLIANCE

Dosing compliance for a specified period is defined as the number of capsules actually taken by a patient during that period divided by the number of capsules prescribed for the same period multiplied by 100. The total number of capsules actually taken during a specific time period will be calculated from the study medication records. The number of capsules expected to be taken for a specific treatment period will be calculated by multiplying the number of days in that period by the number of capsules prescribed to be taken per day.

Descriptive statistics for investigational product compliance during the double-blind treatment period will be presented by treatment group for each period between 2 consecutive visits, as well as for the whole double-blind treatment period, for the Safety Population.

10.0 EFFICACY ANALYSES

The efficacy analyses will be based on the ITT Population. *Baseline* for efficacy is defined as the last non-missing efficacy assessment recorded at or prior to first dose of investigational product. All statistical tests will be 2-sided hypothesis tests performed at the 5% level of significance for main effects. All confidence intervals will be 2-sided 95% confidence intervals, unless stated otherwise.

For efficacy analyses in which study center is a factor, a small center will be defined as a center with fewer than 2 patients in any treatment group in the ITT Population. Small centers will be pooled to form pseudo-centers so that each treatment group includes at least 2 ITT patients within the center. Pooling will be done using the following algorithm:

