Based on the number of ITT patients, small centers will be ordered from the largest to the smallest, and centers of the same size will be ordered from the largest center code to the smallest center code. The pooling process starts with the largest small center from the top, hich will be pooled with the smallest from the bottom until a non-small pseudo center is formed. The process will be repeated using the small centers left out after the first pass. If any centers are left out at the end of the process, they will be pooled with the smallest pseudo center. If there is more than 1 smallest pseudo center, the pseudo center with the smallest center code will be selected. In case that the pseudo center formed by pooling all small centers is still a small center, it will be pooled with the smallest non-small center. If there is more than 1 smallest non-small center, the one with the smallest center code will be selected.

These pseudo-centers will be used for all efficacy analyses when the model is adjusted for study center.

By-visit analyses based on the mixed-effects model for repeated measures (MMRM) using the observed case (OC) approach will be performed for all continuous efficacy parameters with multiple post-baseline measurements.

In addition, by-visit analyses using the last-observation-carried-forward (LOCF) approach will be presented for all efficacy parameters. For the LOCF approach, only the postbaseline total score of a parameter will be imputed; individual item scores will not be carried forward to derive the total score. Baseline total score will be carried forward only for the intermittent missing scores immediately after baseline. If all the postbaseline values are missing, the baseline value will not be carried forward.

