The LOCF approach is based on an analysis-of-covariance (ANCOVA) model including treatment group and pooled study center as factors and baseline CDRS-R total score as a covariate. The pattern-mixture model approach is based on the non-future dependent missing value restrictions (Kenward et al., 2003) and is performed to assess the robustness of the primary MMRM results to the possible violation of the missing-atrandom assumption. The pattern for the pattern-mixture model will be defined by the patient's last visit with an observed value. The observed CSRS-R total score at a visit is assumed to have a linear relationship with the patient's prior measurements. The missing values will be imputed under the assumption that the distribution of the missing observations differs from that of the observed only by a shift parameter value Δ . The dataset with all missing values imputed will be analyzed using an ANCOVA model with treatment group and pooled study center as factors and baseline CDRS-R total score as a covariate for between-treatment group comparisons at Week 8. The imputation of missing values and the analysis will be performed multiple times and the inference of this sensitivity analysis will be based on the combined estimates using the standard multiple imputation technique. The range of values for the shift parameter Δ is selected as 0 to 6 based on experience with historical data. Technical details of the proposed patternmixture model approach (e.g., the models for the pattern-specific identifiable densities and the unidentified conditional distributions, the shift parameter Δ , and the multiple imputation algorithm) are provided in Appendix I to this SAP.

Graphical display of treatment difference vs. placebo (mean difference \pm SE) in primary efficacy parameter will be provided by pooled study center to examine the consistency of the primary efficacy results across study centers.

The site 0070 ceased operations on October 31, 2020, due to the damage caused by Hurricanes Laura and Delta, which made landfall on August 27, 2020 and October 10, 2020, respectively. One more sensitivity analysis excluding all data from this site will be performed on the primary efficacy parameter. The same MMRM would be applied on all OC of change from baseline to Week 8 in CDRS-R total score except all values of Site 0070.

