$$\omega_{s-1,j} = \frac{\alpha_j f(y_1, ..., y_{s-1} \mid L = j)}{\sum_{t=s-1}^{T} \alpha_t f(y_1, ..., y_{s-1} \mid L = t)}, \text{ and } \alpha_j \text{ represents the fraction of}$$

$$(4)$$

patients from Pattern *j*.

Each factor of the unidentifiable conditional distribution of y_s ($s \ge t + 2$) on the right side of (1) can be expressed using the following:

- $f(y_s | y_1,...,y_{s-1}, L = s-1)$, the unidentifiable conditional distribution of the first missing in pattern s-1,
- $f(y_s | y_1,...,y_{s-1}, L = j)$, the identifiable conditional distributions of y_s given $y_1,...,y_{s-1}$ of pattern j ($j \ge s$), and
- α_i , the fraction of patients from pattern j ($j \ge s 1$).

So under NFD, all the unidentifiable conditional distribution on the right side of (1) can be estimated and missing value could be therefore imputed based on the assumption for unidentifiable conditional distribution of the first missing.

We re-formulate the partition in (3), for $s \ge t + 2$, as the following:

$$f(y_s \mid y_{I},..., y_{s-1}, L = t) = \delta_{s-1} f(y_s \mid y_{I},..., y_{s-1}, L = s - 1) + (I - \delta_{s-1}) f(y_s \mid y_{I},..., y_{s-1}, L \ge s)$$
(5)

for $s \ge t + 2$ with $\delta_{s-1} = \omega_{s-1,s-1}$.

Therefore, under monotone missing and NFD assumption, the unidentifiable conditional densities for Visit s in Pattern t ($s \ge t + 2$) can be expressed as a mixture distribution of $f(y_s \mid y_1,...,y_{s-1}, L = s - 1)$ - the unidentifiable conditional distribution of the first missing measurement y_s in Pattern s - 1, and $f(y_s \mid y_1,...,y_{s-1}, L \ge s)$ - the identifiable conditional distribution of y_s from all the patterns with observed data at Visit s or beyond:

$$f(y_s \mid y_l, ..., y_{s-l}, L \ge s) = \sum_{j=s}^{T} \lambda_{s-l,j} f(y_s \mid y_l, ..., y_{s-l}, L = j)$$
 (6)

where the mixture probability

$$\lambda_{s-l,j} = \omega_{s-l,j} / (1 - \omega_{s-l, s-l}) = \frac{\alpha_j f(y_l, ..., y_{s-l} \mid L = j)}{T} \quad \text{for } j \ge s, \text{ where } \alpha_j \text{ is the fraction of}$$

$$\sum_{t=s}^{T} \alpha_t f(y_l, ..., y_{s-l} \mid L = t)$$
(7)

patients from Pattern *j*.

The conditional densities for the first missing are selected as:

$$f(y_s | y_{l,...}, y_{s-1}, L = s - 1) = f(y_s - \Delta | y_{l,...}, y_{s-1}, L \ge s)$$
 for $s = 2, ..., T$, (8)

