Note that the two distributions only differ by a shift (Δ) parameter. When $\Delta = 0$, the missing value y_s in Pattern s-I is imputed based on the distribution of all observed data up to Visit s, as a result, leading to missing at random (MAR) missingness. When $\Delta \neq 0$, (8) will introduce a scenario of MNAR. The similar idea was also presented in the recent publication "The Prevention and Treatment of Missing Data in Clinical Trials" by the National Academies Press. The selection of the plausible values for the shift parameter (Δ) is discussed in Section 3.0.

Note that per recommendation in Wang and Daniels (2011), only the observed data within pattern is assumed to be multivariate normal. The observed data distribution can be expressed in terms of the marginal distribution of baseline measurement and the conditional distributions of postbaseline measurements given earlier measurements. Assuming that these distributions are normal, the linear regression of each observation on prior observations will yield least-squares estimates of model parameters that can be utilized for independent posterior draws of model parameters for observed data. Multiple imputation approach will be used to estimate the overall mean at the final time point.

2. Imputation Procedure

All the missing data will be imputed to create complete datasets, then statistical analysis can be performed using appropriate techniques such as ANCOVA. The imputation can accommodate MNAR missing data mechanisms, based on the theory discussed in the previous section.

The model parameters for each dropout pattern, i.e., the mean, variance and proportions of observations in each pattern, are drawn from their posterior distributions prior to the imputation of missing data for a single imputation.

The details of imputation within a pattern, say Pattern *t*, are as the following:

Step 1. Impute the first missing value y_{t+1} for each patient in Pattern t (t = 1,..., T-1):

- a. Compute estimates of mixture probabilities $\lambda_{s-l,j}$ in (7) with s = t+1 given the posterior draw of proportions of observations in each pattern and the posterior draw of regression parameters for the observed data.
- b. Draw a random integer from $\{s,...,T\}$ to index a component distribution on the right hand side of (6), using mixture probabilities obtained in a). Draw y_{t+1}^* from the identified component normal distribution. Impute the missing y_{t+1} as $\widetilde{y}_{t+1} = y_{t+1}^* + \Delta$.

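### The pattern-mixture check on informative dropout leaves out dosed patients who never had a postbaseline CDRS-R, although its algorithm could probably impute them; the effect is small and the repair cheap

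*SAP*

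**What the plan says.** - **Population.** SAP 6.4 takes as ITT "all patients in the Safety Population who had the baseline and at least 1 postbaseline assessment of the CDRS-R total score". Protocol 9.7.1.4 has the same rule. SAP 10.0 then states: "The efficacy analyses will be based on the ITT Population". Neither SAP 10.1 nor Appendix I names another population for the pattern-mixture analysis.
- **Purpose of that analysis.** SAP 10.1 says that it "is performed to assess the robustness of the primary MMRM results to the possible violation" of the missing-at-random assumption.
- **Patterns.** SAP 10.1: "The pattern for the pattern-mixture model will be defined by the patient's last visit with an observed value". Appendix I builds the observed-data distribution from the "marginal distribution of baseline measurement and the conditional distributions of postbaseline measurements given earlier measurements", and it imputes Patterns t = 1 to T-1.
- **Shift.** Appendix I introduces the rule with "The conditional densities for the first missing are selected as", followed by a version of the observed density shifted by Δ, for s = 2 to T. SAP 10.1 sets the size: "The range of values for the shift parameter Δ is selected as 0 to 6 based on experience with historical data".
- **LOCF.** SAP 10.0 gives no cover either: "If all the postbaseline values are missing, the baseline value will not be carried forward".

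**The concern.** Having a postbaseline rating is an event after randomisation, so this is a modified intent-to-treat set under the name ITT. For a likelihood analysis of observed scores the label matters little. For an imputation analysis it matters more, because that method can give a Week 8 value to someone with only a baseline. The check on informative dropout thus omits the patients with the most missing data. If such patients were more common in one arm, every planned efficacy analysis would share the same selection, and none would show its effect on the estimate.

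**Working it through.** **1. The plan's own figure.** Inputs from SAP 14.0: difference 4, SD 11.1 (4/11.1 = 0.36), 160 per arm, correlation 0.7, dropout 17%, power 85%.
- Two-sample power with no dropout: 89.7%.
- Week 8 completers only (160 × 0.83 = 132.8 per arm): 83.6%.
- MMRM information over 6 postbaseline visits, compound symmetry 0.7, monotone dropout. Each patient adds the inverse of the covariance matrix of the visits observed. The Week 8 variance is the last diagonal element of the inverted sum. With dropout spread evenly the power is 86.7%; other timings give 83.6% to 87.5%. Dropout timing is assumed, as the plan does not state it. The stated 85% is reproduced within 2 points.

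**2. Does the population rule touch the MMRM?** Suppose 5% of each arm (8 of 160) is never rated and the other 12% drop out evenly later. Power is 86.3% with 160 per arm including these patients, and 86.3% when refitted on the 152 who remain. The rule changes nothing here. The GLMM for response and remission (SAP 10.3) also works from observed outcomes, so the same reasoning applies.

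**3. Is there a baseline-only pattern?** Appendix I starts from the baseline distribution, has no y_0, applies the shift from s = 2 and imputes from Pattern 1. With y_1 as baseline there are 7 measurements (baseline and Weeks 1, 2, 3, 4, 6, 8), and Pattern 1 means baseline only. SAP 6.4 makes that pattern empty. This is an inference: Appendix I never writes that y_1 is baseline.

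**4. How many patients?** The documents give no rate. 0.17 × 160 = 27 dropouts per arm. If 10% to 30% of them were never rated (assumed), that is 3 to 8 per arm, or 2% to 5%.

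**5. How far would the sensitivity estimate move?** Assume that, apart from Δ, imputed values match those of rated patients in the same arm. Then

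movement = (share never rated on levomilnacipran − share on placebo) × (part of Δ left at Week 8).

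Appendix I adds Δ in full only at the first missing visit. Later visits inherit it through regression on earlier values, and receive Δ again only with a mixture probability, taken here as 0 to 0.05 (assumed; 0.05 × 6 = 0.3 per visit). For Δ = 6:
- *Compound symmetry 0.7* (extended to baseline, assumed). With k earlier values, each has coefficient 0.7/(1 + 0.7(k − 1)). At probability 0, Week 2 gets 6 × 0.7/1.7 = 2.47, and the shift stays at 2.47 to Week 8. At 0.05, Weeks 2 to 8 get 2.77, 2.86, 2.93, 2.98 and 3.03.
- *AR(1) 0.7.* At probability 0: 6 × 0.7^5 = 1.01. At 0.05: 1.01 + 0.3 × (1 − 0.7^5)/0.3 = 1.84.

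| Imbalance between arms (assumed) | Movement at Δ = 6 | Ceiling (full 6 persists) |
|---|---|---|
| 2 points | 0.02 to 0.06 | 0.12 |
| 3 points | 0.03 to 0.09 | 0.18 |
| 5 points | 0.05 to 0.15 | 0.30 |

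At 3 points, 0.03/4 to 0.09/4 is about 1% to 2% of the planned effect. With equal shares the movement is about zero.

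**The case against.** The case for leaving the plan alone has several sound parts.

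- **Early leavers are mostly kept.** Protocol 9.3.3 and 9.5.5.6 call for a final visit with a CDRS-R whatever the reason for stopping. Protocol 2.1 and 9.1.1 allow remote rating. SAP Table 16-1 assigns Days 2 to 11 to Week 1, so a patient who stops on Day 4 and is rated at early termination is in ITT. A reader might infer that early intolerance by itself removes a patient; the documents do not support that. Never-rated patients remain possible, because protocol 9.3.3 provides for patients who are lost or do not return, and protocol 9.5.1 bars ratings without the consented caregiver.
- **Nothing is contradictory or hidden.** Protocol and SAP agree. SAP 7.0 tabulates the Randomized, Safety and ITT populations by arm, and SAP 8.0 gives demographics for both Safety and ITT. That shows how many are excluded, but not what they would do to the estimate.
- **The baseline-only pattern is inferred.** If y_1 were the first postbaseline visit, Appendix I would have no such pattern. The text favours baseline. On either reading the exclusion itself stands.
- **Larger effects do not follow.** A reader might suppose no change in never-rated patients and improvements of 15 to 25 points in the others (assumed), giving 0.03 × 15 = 0.45 to 0.03 × 25 = 0.75 points. Appendix I does not impute no change; it draws from observed patients and adds at most 6, so it could not produce that shift. Likewise, a response gap of 50% against 40% would shrink to 0.95 × 50 − 0.98 × 40 = 8.3 points only under a non-responder rule that the plan does not use, with assumed rates.
- **The Safety Population is itself selected after randomisation.** This is correct, and the fix should allow for it.

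**Conclusion.** The point holds as a small gap in one sensitivity analysis. The pattern-mixture check omits dosed patients with no postbaseline CDRS-R, and on the better reading of Appendix I its algorithm could include them. The primary MMRM estimate, its power and the planned GLMM are unaffected, so nothing here supports a claim that the primary result is biased by this rule.

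For an assumed imbalance of 3 percentage points, the pattern-mixture difference at Week 8 moves by about 0.03 to 0.09 points at Δ = 6, with a ceiling of 0.18. This rests on assumptions that the documents do not settle: the share of never-rated patients and its imbalance, the correlation pattern, the mixture probabilities, a common Δ in both arms, and imputed values that otherwise match the rated patients of the same arm. The reason to act is completeness of the check at little cost, not the expected size.

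**What to change.** 1. Keep the ITT Population for the MMRM.
2. In SAP 10.1, run the pattern-mixture analysis on all patients with a baseline CDRS-R. The Safety Population is the minimum. All randomised patients would be better, since those never dosed are otherwise left out too. For them, baseline needs the Visit 2 anchor of protocol 9.7.5, because SAP 10.0 ties baseline to the first dose.
3. State in Appendix I that y_1 is baseline, so that Pattern 1 is baseline only.
4. Record the different population in SAP 18.0, which now lists no changes from the protocol.
5. Optionally, add a supportive summary of response and remission that counts never-rated patients as non-responders and non-remitters.

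The cost is some SAP wording and one population flag. The downside is that a few fully imputed patients make the sensitivity estimate slightly less precise.

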7.0 PATIENT DISPOSITION

The number and percentage of patients in 3 of the study populations (Randomized, Safety, and ITT) will be summarized by treatment group and study center; the Screened Population will be summarized overall only by study center.

Screen-failure patients (i.e., patients screened but not randomized) and the associated reasons for failure to randomize will be tabulated overall for all the screened patients.

The number and percentage of patients who complete the double-blind treatment period and of patients who prematurely discontinue during the same period will be presented for each treatment group and pooled across treatment groups for the Safety Population. The number and percentage of patients who enter the double-blind down-taper period and of patients who complete the double-blind down-taper period will be presented for each treatment group and pooled across treatment groups for the Safety Population.

The reasons for premature discontinuation from the double-blind treatment period as recorded on the disposition pages of the electronic case report forms (eCRF) will be summarized (number and percentage) by treatment group for the Safety Population. Percentage of premature discontinuations will be provided for overall and for each discontinuation reason. All patients who prematurely discontinue during the double-blind treatment period will be listed by discontinuation reason for the Safety Population.

8.0 DEMOGRAPHICS AND OTHER BASELINE CHARACTERISTICS

Demographic parameters (age; age group [7-11 and 12-17]; sex; race; ethnicity), and baseline characteristics (weight; height; and body mass index (BMI)) will be summarized descriptively by treatment group for the Safety and ITT populations, respectively. Baseline efficacy variables will be summarized by treatment group for the ITT population.

Continuous variables will be summarized by number of patients and mean, SD, median, Q1, Q3, minimum, and maximum values. Categorical variables will be summarized by number and percentage of patients.

Abnormalities in patients' medical and surgical histories will be coded using the *Medical Dictionary for Regulatory Activities (MedDRA)*, version 22.0 or newer. The number and percentage of patients with abnormalities in medical and surgical histories in each system organ class and preferred term will be summarized by treatment group for the Safety Population. MDD history and nondrug psychiatric treatment history will also be summarized by treatment group for the Safety Population.

The World Health Organization Drug Dictionary, version March 2017 or newer, will be used to classify prior and concomitant medications by therapeutic class and drug name.

Prior medication is defined as any medication taken before the date of the first dose of double-blind investigational product. Concomitant medication is defined as any medication taken on or after the date of the first dose of double-blind investigational product. Both prior and concomitant medications use will be coded by drug name and therapeutic class. The use of prior and concomitant medications will be summarized by the number and percentage of patients receiving each drug within each therapeutic class in each treatment group for the Safety Population. If a patient took a specific medication multiple times or took multiple medications within a specific therapeutic class, that patient would be counted only for the coded drug name or therapeutic class.

Summaries of concomitant medication use will be presented for the double-blind treatment period and the double-blind down-taper period, separately. Any concomitant medications started after the date of the last dose of double-blind investigational product in the study will not be presented in the summary tables but will be included in the patient data listings.

9.0 EXTENT OF EXPOSURE AND TREATMENT COMPLIANCE

9.1 EXTENT OF EXPOSURE

Exposure to the investigational product for the Safety Population during the double-blind treatment period will be summarized in terms of treatment duration, calculated as the number of days from the date of the first dose of double-blind investigational product to the date of the last dose of double-blind investigational period, inclusive. Descriptive statistics (number of patients, mean, SD, median, Q1, Q3, minimum, and maximum) will be presented by treatment group. The number and percentage of patients will be presented for specific intervals of exposure by treatment group.

Patient-years, defined as total exposure to the double-blind investigational product in years (excluding the double-blind down-taper period), will be summarized by treatment for the Safety Population.

In addition, weekly and overall mean daily dose of investigational product during the double-blind treatment period will be summarized by treatment group for the Safety population.

